
STATISTICS/SAMPLE SIZE ESTIMATE
	
Statistics: All baseline subject characteristics will be summarized in a tabular format. Safety data will be described for all subjects receiving at least one dose of DFMO. Safety data will include values for hematology, serum chemistry, vital signs, and adverse events. The proportion of subjects experiencing adverse events, serious adverse events, and treatment delays will be summarized for each dosing cohort.
 
Sample Size: Stratum 1: A 70% 2-year EFS rate was selected as the Phase I baseline rate. The baseline 70% EFS rate at 2-years was based upon published data by Yu et al. It is hypothesized that DFMO will increase the 2-year EFS rate to 80% which represents an approximately 10% increase in the duration of the EFS rate at 2-years. Assuming a directional 5% one population binomial test, a sample size of $n = 127$ patients will be required to achieve an 80% power to detect this 2-year difference in EFS (70% vs 80%).
 
The comparison of the biomarker prevalence rates assumes that the Stratum 1 cohort will experience a relapse rate of 30% and a 70% non-relapse rate at up to two years of follow-up. It is also assumed that the corresponding prevalence of an elevated biomarker will be 60% for the relapse group and 30% in the non-relapse group, respectively. This hypothesized prevalence difference will be detectable with at least an 85% power with an overall sample size of $N=127$ patients (38 relapse and 89 non-relapse) using a Fisher’s Exact Test and a non-directional Type I Error level of 5%.
 
Stratum 2: Examination of EFS will require a sample size of $n = 33$ subjects in Stratum 2 to test whether treatment with DFMO can prolong the overall estimated EFS at two years to 30% from the 10% at two years estimate for the known historical data in this subject population. A one population binomial test with power 80% and a 5% two-tailed Type I error level will require $n = 33$ total patients
 
The one population binomial test will reject the null hypothesis that the two year EFS rate = 10% in favor of the EFS = 30% if 7 or more of the $n = 33$ patients are observed to have at least a two year EFS.

---	--

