Based upon tabled median EFS times all patients presented by Santana et al. (Cancer, June 15, 2008) for first and second recurrence times, a median first recurrence time of 8.7 months is equivalent to a 14.8% EFS at two years, and the median time to a subsequent second recurrence of 3.8 months is equivalent to an EFS rate of 1.3% at two years assuming an exponential time-to-event model. Assuming that two thirds of the relapse patient population will have had only a single relapse and that the other third of the patients will have had two or more relapses, then a weighted average of these two EFS rates (14.8% and 1.3%) equals 10.3%. A 10% historical EFS rate for two years was assumed for simplicity. Examination of an increase in EFS will require a sample size of n = 33 subjects in Stratum 2 to test whether treatment with DFMO can prolong the overall estimated EFS at two years to 30% from the 10% two years estimate for the above historical data in this patient population. The sample size is based upon a one sample binomial test of proportions with a power 80% and a 5% two -tailed Type I error level.

An observation of 7 or more patients with at least a two year EFS rate out of the $n = 33$ patients will result in the rejection of the null hypothesis of a 10% EFS in favor of the alternative of a 30% two year EFS rate. An exact binomial 95% confidence interval for the two year estimated EFS will complement the prior formal two-stage hypothesis test. Since the actual EFS time-to-event data is derived from the times to recurrence, a Kaplan-Meier analysis of the time-to-event data analysis will be conducted, and the median time to recurrence and a 95% confidence for this value will be obtained to supplement this EFS point estimate. Since this group of Stratum 2 patients will consist of patients with prior single and multiple recurrence histories, EFS and time to event data will be examined by prior recurrence histories. In particular, the impact of prior recurrence history on the time to recurrence will be explored using Kaplan-Meier analysis and Cox proportional hazard models. The response to DFMO therapy and subsequent recurrences will also be explored in combination with prior recurrence histories using Cox models.

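### Stratum 2's cut-off of 7 of 33 does not match its stated 5% two-tailed, 80%-power test, and at exactly 7 the standard exact 95% interval still contains the 10% null.

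*Combined protocol and SAP*

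**What the plan says.** The Stratum 2 design appears in the synopsis (Statistics/Sample Size Estimate) and in section 10.3 (Sample Size and Analysis, Stratum 2).

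- **Hypotheses.** The null comes from published recurrence times: "A 10% historical EFS rate for two years was assumed for simplicity". The aim is to "prolong the overall estimated EFS at two years to 30% from the 10% two years estimate".
- **Test and size.** Section 10.3 bases n = 33 on a "one sample binomial test of proportions with a power 80% and a 5% two -tailed Type I error level". The synopsis agrees: "A one population binomial test with power 80% and a 5% two-tailed Type I error level will require" 33 patients.
- **Decision rule.** In section 10.3, "An observation of 7 or more patients with at least a two year EFS rate out of the" 33 leads to rejection. In the synopsis, the null is rejected "if 7 or more of the $n = 33$ patients are observed to have at least a two year EFS".
- **Interval.** "An exact binomial 95% confidence interval for the two year estimated EFS will complement the prior formal two-stage hypothesis test".

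Neither place gives the attained error or power of the rule, or says which two-sided exact convention is meant. For Stratum 1 the same sections call the test directional, so the two-tailed label for Stratum 2 reads as deliberate.

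**The concern.** The cut-off is the whole formal decision rule for Stratum 2 on the primary endpoint. The figures printed beside it describe a two-tailed 5% test with 80% power, but the number itself is the cut-off of a one-sided 5% test.

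This would matter at the boundary. With exactly 7 of 33 event-free at two years, the report would reject a 10% rate and, next to that, would probably show an exact 95% interval that includes 10%. Someone would then have to choose a convention with the result in hand.

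**Working it through.** **Inputs.** p0 = 0.10, p1 = 0.30, n = 33, cut-off 7, 5% two-tailed, power 80%, exact 95% interval. All are from the synopsis and section 10.3.

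**1. The null.** Under the exponential model:
- 0.5^(24/8.7) = 14.8%
- 0.5^(24/3.8) = 1.3%
- (2 × 14.8 + 1.3)/3 = 10.3%, which the plan rounds to 10%.

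These figures reproduce.

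**2. The sample size.** Take the equal-tailed reading, in which the upper tail may hold at most 0.025. For each n, find the smallest r with P(X ≥ r | 0.10) ≤ 0.025, then the power P(X ≥ r | 0.30).

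| n | r | Upper tail at 10% | Power at 30% |
|---|---|---|---|
| 29 | 7 | 0.0216 | 0.812 |
| 30 | 8 | 0.0078 | 0.719 |
| 32 | 8 | 0.0117 | 0.788 |
| 33 | 8 | 0.0141 | 0.818 |
| 34 | 8 | 0.0169 | 0.844 |

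Power first passes 80% at n = 29 and then drops back. From n = 33 it stays at or above 80% (checked to n = 41). So n = 33 with about 80% power reproduces, and the cut-off that goes with it is **8**.

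**3. The printed cut-off at n = 33.**

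| Rule | P(reject at 10%) | Twice the upper tail | Power at 30% | Clopper-Pearson 95% interval at the cut-off |
|---|---|---|---|---|
| X ≥ 7 | 0.0417 | 0.083 | 0.906 | 9.0% to 38.9% |
| X ≥ 8 | 0.0141 | 0.028 | 0.818 | 11.1% to 42.3% |

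The upper tail at 7 is 0.0417/0.025 = 1.7 times the equal-tailed limit. The interval at 7 contains 10%; the interval at 8 does not.

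**4. The minimum-likelihood two-sided reading.** This p-value adds every outcome no more probable under the null than the one observed. Under 10%, P(X = 0) = 0.9^33 = 0.0309 and P(X = 7) = 0.0276. Zero is therefore not counted, and p at 7 is 0.0417, which rejects. On this reading the power at n = 33 is 0.906, and 80% is first reached at n = 25 (cut-off 6, error 0.033, power 0.807) and held from n = 29.

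The result also depends on rounding the null. At 10.3%, P(X = 0) = 0.897^33 = 0.0277, while P(X = 7) = 4,272,048 × 0.103^7 × 0.897^26 = 0.0311. Zero is now counted, so p = 0.0478 + 0.0277 = 0.0755, which does not reject.

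**5. Reach.** Only X = 7 is decided differently by the two cut-offs. P(X = 7) is 0.028 at a true 10% and 0.088 at a true 30%.

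**6. If more than 33 are analysed.** The synopsis enrols 38 to secure 33 evaluable. With 7 carried over unchanged, P(X ≥ 7 | 0.10) is 0.055 at n = 35 and 0.080 at n = 38, above 5% on any reading.

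**The case against.** The strongest reply has four parts.

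- **The 5% is not breached.** The plan never states a 2.5% upper-tail limit, and the rule's total error at n = 33 is 4.17%. With 33 patients an equal-tailed test cannot reject downwards at all, because P(X = 0) = 0.031 exceeds 0.025; the rule of 8 or more is in effect a 1.4% test. The minimum-likelihood test is a recognised two-sided method and rejects at 7. All of this stands.
- **n = 33 does not single out 8.** An equal-tailed test already has 81.2% power at n = 29, so the claim that 33 are required is not literally true there either. That is correct. The attained power, 81.8% against 90.6%, is what points to 8. If 80% is only a floor, 90.6% meets it, but then 33 patients were not needed to reach it.
- **The interval is not named.** Exact could mean an interval inverted from the minimum-likelihood test, whose lower limit is about 10.15% and excludes 10%. Clopper-Pearson is the usual default, and the Blaker interval (lower limit about 9.65%) also contains 10%. The conflict is likely but depends on the convention.
- **Moving a threshold is not trivial.** The trial is open label, and the pharmacokinetic sections speak of currently enrolled subjects. Changing a success criterion at that stage needs justification. This bears on which fix to choose, not on whether one is needed.

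None of these makes the cut-off of 7, the two-tailed label, 80% power and a required n of 33 hold together.

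**Conclusion.** The concern holds. As printed, the Stratum 2 rule behaves as a one-sided 5% test (attained 4.17%) with 90.6% power. The test described beside it, read as equal-tailed, has a cut-off of 8 with an upper tail of 1.41% and 81.8% power. Read by minimum likelihood, the cut-off of 7 is right, but the power and sample-size statements are not.

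The conclusion assumes exact binomial calculation, the 10% null as stated, and 33 patients with known two-year status. The conflict with the interval further assumes Clopper-Pearson. The practical reach is a single outcome, 7 of 33, and total error at n = 33 does not exceed 5%. Even so, it is the threshold for a primary-endpoint claim and must be settled before the data are examined.

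**What to change.** Choose one option and apply it in both the synopsis and section 10.3.

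- **Option A:** change the cut-off to 8 or more. State the upper-tail error of 1.4%, the power of 81.8%, and that the interval is Clopper-Pearson 95%.
- **Option B:** keep 7 or more. Call the test one-sided 5%, state the attained error of 4.2% and power of 90.6%, and pair it with a one-sided 95% lower bound (10.4% at 7 of 33, which excludes 10%).

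Option B leaves the success threshold alone and is the lower-risk choice if any Stratum 2 outcomes have been seen.

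State the cut-off for the number actually analysed:

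| n analysed | Option A (upper tail ≤ 2.5%) | Option B (upper tail ≤ 5%) |
|---|---|---|
| 33–34 | 8 | 7 |
| 35–36 | 8 | 8 |
| 37–38 | 9 | 8 |

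Also remove the description of the test as two-stage, or define the stages. Section 10.3 mentions interim analysis time points, but no first-stage size or boundary is given for Stratum 2.

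The cost is a few words and one number in two places, with no extra patients. Option A gives up about 9 points of power that the plan never claimed (90.6% to 81.8%) and still meets the stated 80%.

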	
Subjects will be evaluated in 2 strata:
 
 • Stratum 1: Subjects that are in remission at the end of upfront therapy defined as chemotherapy (5-7 cycles), surgery as indicated, consolidation therapy as indicated, radiation therapy as indicated, anti-GD2 antibody therapy with retinoic acid up to 6 cycles. • Stratum 2: Subjects that are in remission after any previous relapse or refractory therapy 
Stratum 1- A total of 127-140 subjects in Stratum 1 will be enrolled to ensure that there will be 127 evaluable subjects.
 
Stratum 2- A total of 38 subjects in Stratum 2 will be enrolled to ensure that there will be 33 evaluable subjects.

ELIGIBILITY
	
Inclusion Criteria
 
 1. Age: 0-21 years at the time of diagnosis. 2. Diagnosis: histological verification at either the time of original diagnosis or a previous relapse of high risk neuroblastoma. 3. Disease Status: Neuroblastoma that is in Remission 4. Greater than 30 days from completion of cytotoxic and antibody therapy and less than 120 days from previous therapy. 5. A negative serum or urine pregnancy test is required for female subjects of child bearing potential (onset of menses or ≥ 13 years of age). 6. Both male and female post-pubertal study subjects need to agree to use one of the more effective birth control methods during treatment and for six months after treatment is stopped. These methods include total abstinence (no sex), oral contraceptives (“the pill”), an intrauterine device (IUD), levonorgestrol implants (Norplant), or medroxyprogesterone acetate injections (Depo-provera shots). If one of these cannot be used, contraceptive foam with a condom is recommended. 7. ANC > 500/μl and platelet count >50,000/μl 8. Organ Function Requirements

Subjects must have adequate liver function as defined by
 AST and ALT <10x upper limit of normal
 Serum bilirubin must be ≤ 2.0 mg/dl
 Serum creatinine based on age/gender as follows:

Age	Maximum Serum Creatinine (mg/dL)	
	Male	Female
1 month to < 6 months	0.4	0.4
6 months to < 1 year	0.5	0.5
1 to < 2 years	0.6	0.6
2 to < 6 year	0.8	0.8
6 to < 10 years	1	1
10 to < 13 years	1.2	1.2
13 to < 16 years	1.5	1.4
≥ 16 years	1.7	1.4

9. Informed Consent: All subjects and/or legal guardians must sign informed written consent. Assent, when appropriate, will be obtained according to institutional guidelines

Exclusion Criteria

1. Lansky score < 60%

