10.2 Statistical Analysis

This is an open label, single agent, multicenter, study for patients with neuroblastoma that are in remission.

The following data sets will be used in this study:

- All enrolled and eligible subjects (ITT) population: All eligible subjects who have a signed informed consent form.
- All treated and eligible subjects (Safety evaluable) population: All subjects who received at least one dose of study drug
- All eligible subjects treated to first evaluable time point with evaluation completed (generally 3 cycles) (as Treatment Efficacy) population, unless subjects have reached the study endpoint of progression of disease at an earlier time point.

Efficacy analyses will be performed on the Treatment evaluable population. Safety analysis will be performed on the Safety and Efficacy evaluable population.

10.3 All baseline patient characteristics will be summarized in a tabular format. Safety data will be described for all subjects receiving at least one dose of DFMO. Safety data will include values for hematology, serum chemistry, vital signs, and adverse events. The proportion of subjects experiencing adverse events, serious adverse events, dose limiting toxicities and treatment delays will be summarized. Enrollment to study will not pause at interim analysis time points.

Sample Size and Analysis:

Stratum 1:

A 70% 2-year EFS rate was selected as the Phase I baseline rate. The baseline 70% EFS rate at 2-years was based upon published data by Yu et al. (82). It is hypothesized that DFMO will increase the 2-year EFS rate to 80% which represents an approximately 10% increase in the duration of the EFS rate at 2-years. Assuming a directional 5% one population binomial test, a sample size of $n = 127$ patients will be required to achieve an 80% power to detect this 2-year difference in EFS (70% vs 80%).

The comparison of the biomarker prevalence rates assumes that the Stratum 1 cohort will experience a relapse rate of 30% and thus a 70% non-relapse rate at up to two years of follow-up. It is also assumed that the corresponding prevalence of an elevated biomarker will be 60% for the relapse group and 30% in the non-relapse group, respectively. This hypothesized prevalence difference will be detectable with 85% power with an overall sample size of N=127 patients (38 relapse and 89 non-relapse) using a Fisher's Exact Test and a non-directional Type I Error level of 5%.

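### Stratum 2's only success rule is a fixed count of 7 tied to 33 patients, but 38 are enrolled and all evaluable patients are analysed, so the rule does not fit the analysis set if more than 33 are evaluable

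*Combined protocol and SAP*

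**What the plan says.** - **Enrolment** (synopsis, Study Design): "A total of 38 subjects in Stratum 2 will be enrolled to ensure that there will be 33 evaluable subjects". Read plainly, 33 is a floor.
- **Analysis set** (section 10.2): "Efficacy analyses will be performed on the Treatment evaluable population". Eligible patients enter that set once treated to their first evaluation with it completed, generally three cycles, or if they progress sooner. The set has no upper limit.
- **Hypotheses** (Sample Size and Analysis, Stratum 2, under 10.3): DFMO is to "prolong the overall estimated EFS at two years to 30% from the 10% two years estimate".
- **Test** (same place): a "one sample binomial test of proportions with a power 80% and a 5% two -tailed Type I error level". An exact binomial 95% confidence interval is to accompany it.
- **Size** (same place): "Examination of an increase in EFS will require a sample size of n = 33 subjects in Stratum 2".
- **Decision rule** (same place): "An observation of 7 or more patients with at least a two year EFS rate out of the" 33 leads to rejection of the null. The synopsis repeats it: the null is rejected "if 7 or more of the $n = 33$ patients are observed to have at least a two year EFS".

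The documents do not restrict the test to the first 33 evaluable patients, give a count for another denominator, or say that the count will be re-derived.

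**The concern.** The success rule and the analysis set are defined on different numbers. The rule needs exactly 33 patients, while the analysis set could hold any number up to 38. An early relapse does not make a patient non-evaluable, so more than 33 evaluable is a realistic outcome.

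EFS is the primary endpoint, and this count is the only formal success criterion for Stratum 2. The trial is open label, so if the denominator is not 33, the choice of what to do will be made with outcomes visible. A reader who takes the printed count at face value with 36 evaluable patients would call 7 a success, although the exact test at 36 does not reject.

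**Working it through.** **Inputs.** Null two-year EFS 10%, alternative 30%, 5% two-tailed, power 80%, n = 33, count 7 (synopsis and Stratum 2 text under 10.3); 38 enrolled (synopsis). The evaluability rate is not given and is varied below.

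**Formula.** P(X ≥ k | n, p) = Σ from x = k to n of C(n, x) pˣ (1 − p)ⁿ⁻ˣ, with p = 0.10 for the type I error and p = 0.30 for power.

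**Step 1: the plan's own figure.** With 2.5% in the upper tail, n = 33 has a critical count of 8, with tail 1.41% and power 81.8%. That agrees with the stated 80%. In the sizes checked (up to 44), 33 is also the smallest n from which exact power stays above 80%: n = 29 reaches 81.2%, but 30 to 32 fall below. So the sample size reproduces with a count of 8. The printed count of 7 at n = 33 has tail 4.17% and power 90.6%, which fits a one-sided 5% test. That sidedness question is separate from the denominator question here.

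**Step 2: carry 7 to other denominators, and re-derive the cut-off at 2.5% in the upper tail.**

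| Evaluable n | P(X ≥ 7) at 10% | Cut-off, 2.5% upper tail | Tail at cut-off | Power at 30% |
|---|---|---|---|---|
| 29 | 2.16% | 7 | 2.16% | 81.2% |
| 30 | 2.58% | 8 | 0.78% | 71.9% |
| 31 | 3.06% | 8 | 0.96% | 75.5% |
| 32 | 3.58% | 8 | 1.17% | 78.8% |
| 33 | 4.17% | 8 | 1.41% | 81.8% |
| 34 | 4.81% | 8 | 1.69% | 84.4% |
| 35 | 5.52% | 8 | 2.00% | 86.7% |
| 36 | 6.28% | 8 | 2.35% | 88.8% |
| 37 | 7.11% | 9 | 0.93% | 82.4% |
| 38 | 8.00% | 9 | 1.11% | 84.8% |

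Keeping 8 at 37 or 38 would give tails of 2.74% and 3.18%. Correcting the count at 33 therefore does not by itself settle the denominator.

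**Step 3: the reading most favourable to the printed count.** A two-sided p-value can be formed by adding every outcome no more likely than the one observed.
- At 33, P(X = 7) = 0.0417 − 0.0141 = 0.0276. Zero successes has probability 0.9³³ = 0.0309, which is larger and is not added, so p = 0.0417 and 7 of 33 rejects.
- At 34, P(X = 7) = 0.0481 − 0.0169 = 0.0312. Zero successes has probability 0.9³⁴ = 0.0278, which is now added, so p = 0.0481 + 0.0278 ≈ 0.076 and 7 of 34 does not reject.

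On this reading the count fails with one extra patient.

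**Step 4: a concrete case.** With 7 successes in 36, the one-sided exact p is 0.063 and the exact 95% interval is 8.2% to 36.0%, which contains 10%. The printed count would still be met.

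**Step 5: how likely other denominators are.** Assume that each of the 38 is evaluable independently with the rate shown. The rate implied by planning 38 for 33 is 33/38 = 86.8%.

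| Assumed rate | Fewer than 33 | More than 33 | 35 or more |
|---|---|---|---|
| 85% | 51% | 31% | 16% |
| 33/38 | 38% | 43% | 25% |
| 90% | 17% | 67% | 46% |
| 95% | 1% | 96% | 88% |

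**The case against.** The strongest reply is that the plan never applies 7 to more than 33 patients. Both statements of the rule name n = 33, and the text gives the test, the null, the alpha and an exact interval, so a careful analyst could derive the cut-off at any n. This stands: the inflation is conditional, and the gap is an unstated choice rather than a planned error.

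Three further points are fair.
- The crossing of 5% at n = 35 uses a one-sided level that Stratum 2 does not declare. Against 2.5% in the upper tail, 7 already exceeds the limit at 33. If the count at 33 were corrected to 8, the remaining excess would be confined to 37 and 38.
- The 8.0% figure needs all 38 to be evaluable. If evaluability is unrelated to outcome (an assumption), a fixed count of 7 averaged over the possible denominators has error P(X ≥ 7 | 38, 0.10 × rate): 3.9% at 85%, 4.3% at 33/38, 5.05% at 90% and 6.4% at 95%.
- At the implied rate, fewer than 33 evaluable (38%) is likelier than 35 or more (25%), so a remedy covering only 33 and above would be incomplete.

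A reader might also infer that evaluable patients would have to be left out to get back to 33. The documents do not support that. Section 10.2 puts all evaluable patients in the efficacy analysis, so dropping any would depart from the plan.

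What the reply does not remove is that one fixed count is printed twice, without a rule for any other number, beside an analysis set that need not be 33.

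**Conclusion.** The point holds as a mismatch between the only stated success rule and the stated analysis set. If 7 is carried to a larger evaluable set, the upper-tail error at 10% is 4.8% to 8.0% for 34 to 38, against 4.2% at 33. Even on the two-sided reading under which 7 of 33 is valid, 7 of 34 is not.

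A reader might conclude that the Stratum 2 test has an 8% type I error. That goes too far: it needs all 38 evaluable and the count left unchanged, and the plan states neither. How often the problem would arise depends on an evaluability rate that the documents do not give; the figures in step 5 rest on independent evaluability at assumed rates.

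The matter is worth correcting before analysis, because the choice would otherwise be made with outcomes known and the correction costs almost nothing.

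**What to change.** In the synopsis and in the Stratum 2 text under 10.3, replace the fixed count with a statement that the exact binomial test against 10% is applied to all evaluable Stratum 2 patients at the realised number, whether below or above 33. It should be at the declared 5% two-tailed level, meaning 2.5% in the upper tail, which matches the exact 95% interval. Print the cut-offs: 7 at n = 29, 8 for n = 30 to 36, and 9 for n = 37 and 38. One set is enough; a one-sided set belongs in the plan only if the declared sidedness is changed.

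State the power as well: at 30% it is at least 81.8% for n = 33 to 38 but 72% to 79% for n = 30 to 32.

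The cost is one sentence and a short table, with no extra patients. These cut-offs take each evaluable patient's two-year status as known. How a patient censored before two years counts in the binomial test still has to be stated separately.
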